## 5.0 STUDY DESIGN AND METHODS

### 5.1 Design / Study Type

This is a pilot RCT to examine the feasibility and acceptability of the 3RP-AYA among approximately 72 adolescent and young adult cancer survivors who are up to 5 years post-treatment. Participants who complete the baseline questionnaire and are randomized will be enrolled and counted toward the accrual goal of 72. As such, up to 72 participants may be enrolled in the study in order to allow approximately 60 patients to participate total in the intervention and waitlist arms (goal of 30 completer-participants per arm). Participants do not need to complete every study measure to be counted towards the 72-participant accrual goal (i.e., participants who only complete some measures/3RP-AYA sessions will still be counted towards the accrual goal); however, patients who do not complete any of the study measures or who do not participate in any intervention visits will not be counted towards this goal.

We plan to examine the proportion of patients who are eligible and the proportion who are found to be ineligible due to age, language, inability to use the videoconferencing software, oncologist refusal, and medically or psychiatrically unable to participate. Out of those who are eligible, we will examine the proportion of enrollments, refusals, lost-to-follow up, withdraws, and study completers. We will examine reasons for and rates of ineligibility and refusal, as these will inform the feasibility of the study and of delivering the program virtually. We will also examine the characteristics of non-completers and the circumstances of non-completion.

### 5.2 Selection of Instruments (refer to section 5.5 for schedule of measures):

**5.2.1 Demographic Survey.** We will gather important demographic information to characterize our sample, including participants’ race, ethnicity, education, relationship status, health insurance, and annual household income (Appendix 8.17).

**5.2.2 Primary Outcomes.** 3RP-AYA Feasibility and Acceptability data will be collected electronically (via REDCap), on paper, or by phone:

**Feasibility:** Feasibility metrics are modeled after resiliency studies led with survivors and other medical populations. We will evaluate program feasibility by examining several process variables, including rates of study eligibility (percent of patients who are eligible), recruitment (number of eligible patients who express interest in our study), enrollment (percent of eligible pool who consents and enrolls), retention (percent of enrollees who complete the follow-up), and treatment adherence (number of days elicited relaxation response, number of participants who complete the follow-up surveys). We will also document reasons for ineligibility and refusal as well as sociodemographic characteristics, medical history, and cancer characteristics of refusers. Additionally, adherence to

recommended RR elicitation will be assessed via Weekly RR practice logs (Appendix 8.27). The Weekly RR practice logs are part of the standard 3RP program, and in order to reduce participant burden, only the questions about weekly RR elicitation, weekly appreciations, and stress, distress, and coping Likert scales are included, while the questions from the standard 3RP weekly practice logs about lifestyle behaviors (exercise and nutrition), social connectedness, and physical/emotional symptoms have been omitted.

**Acceptability:** Intervention acceptability will be assessed at the follow up data collection period with five questions on the 3RP-AYA acceptability questionnaire (Appendix 8.15) rated on a 4-point Likert scale (1=not at all to 4=very much). Items will prompt participants to rate the extent to which they found the program to be 1) enjoyable, 2) helpful, 3) applicable/relevant (i.e., is it appropriate and applicable), 4) convenient (i.e., in regards to delivery modality), and 5) likelihood of future use (e.g., “Will you continue to use RR strategies in the future?”). Treatment satisfaction will be assessed by items on the 3RP acceptability questionnaire which ask participants to rate their level of satisfaction with the following items using a 4-point Likert scale (1= not at all satisfied to 4 = very satisfied): 1) treatment structure, 2) treatment timing (i.e., early survivorship period) and 3) treatment content. We will also qualitatively explore overall satisfaction with three open-ended questions regarding treatment likes, dislikes and recommendations.

**5.2.3. Exploratory Outcomes.** We will collect hair samples for cortisol measurement by mail and psychosocial measures electronically or by mail to determine the preliminary efficacy of this program on stress reactivity and stress management.

**5.2.3a Hair Cortisol Measurement:** Participants will be asked to provide hair samples to measure potential changes in cortisol (“stress hormone”); this method has been used successfully in stress studies and is currently being utilized in our sister 3RP protocols [name] is leading (Partners IRB Protocol #: 2016P001622; DF/HCC #17-063, PI: [name]). Hair grows roughly 1cm/month, thus ensuring sufficient growth for collection. The RA will mail or email detailed sampling instructions (Appendix 8.16) and stamped, addressed envelopes to facilitate returns. Participants will be instructed to provide one hair sample at baseline and one sample at the end of the intervention. Specifically, they will be instructed to cut a small sample of hair (approximately 150 strands, about the diameter of a pencil eraser) from the back of their head, as close to the scalp as possible. They will be asked to tie the strands near the scalp end, place the sample in aluminum foil, and mail to MGH. The hair sampling instructions also include 6 questions about hair care, exercise, and glucocorticoid use, as these can affect hair cortisol measurements. Hair samples will not be collected from participants who have taken glucocorticoid medications (e.g. prednisone) within the past 3 months, as these medications cause cortisol measurements to be inaccurate. However, hair that is chemically treated or dyed may still be used for hair cortisol analysis. We will track the reasons why any hair samples were not collected, as this informs the feasibility and acceptability of hair cortisol collection and analysis for this population.

Rationale for hair cortisol versus salivary cortisol. Recent studies comparing salivary vs. hair cortisol have found that hair samples provide a more robust measure of chronic stress. Specifically, hair cortisol provides a more complete snapshot of cortisol concentration levels across longer periods (e.g., over 3 months) whereas salivary cortisol captures the acute stress response. As such, studies have been more likely to find changes in hair cortisol levels in response to stress management programs. Further, hair sampling may be less burdensome, invasive, and easier to collect than saliva sampling, which requires subjects to provide several samples throughout the day. Saliva sampling is also subject to sampling errors due to incorrect timing, inefficient sampling, and inaccurate collection procedures. We will collect feedback and perceptions of hair sampling measures at study completion. **Sample Processing:** Hair cortisol will be processed by [name] laboratory at the University of Massachusetts, Amherst. Prior to shipping, samples will remain wrapped in aluminum foil, labeled with a study ID and stored at room temperature in a padded envelope.

**5.2.3b Psychosocial Measures.** We will gather relevant information related to current or past levels of distress from participants to examine the psychosocial impact of this program. Information that will be

collected from participants will include symptoms of stress, worrying, anxiety, and depression (Appendix 8.17). These measures take approximately 35 minutes to complete. Participants have the option to skip any questions they prefer not to answer.

- Patient-Reported Outcomes Measurement Information System (PROMIS) Measures: PROMIS is a set of person-centered measures that evaluates and monitors physical, mental, and social health in adults and children. A variety of subscales will be used as exploratory outcomes including, PROMIS Anxiety PROMIS ED Anxiety – short form 4a, PROMIS ED depression – short form 4a, PROMIS ED anger – short form 5a, PROMIS fatigue short form 7b, PROMIS sleep disturbance short form 8a, PROMIS Social Isolation short form 4a
- Coping Self-efficacy Scale: The Coping Self-Efficacy Scale (CSES) is a 26-item measure of perceived self-efficacy for coping with challenges and threats.
- Interpersonal Reactivity Index: The Interpersonal Reactivity Index (Perspective-taking subscale) will be used to measure the level of dispositional empathy participants have. The perspective-taking subscale consists of 7-items and measures the tendency of an individual to take on the perspective of another in daily life.
- Penn State Worry Questionnaire (PSW-Q): The Penn State Worry Questionnaire is a reliable self-report tool used to measure the trait of worry in individuals. The questionnaire consists of 16 items scored on a 5-point scale ranging from 1 (not at all typical of me) to 5 (very typical of me). This measure has been used to differentiate individuals who met varying criteria for general anxiety disorder, indicating the trait of worry is a related, yet independent, aspect of anxiety.
- Visual Analogue Scale 0-10: We are using 5 items rated on a visual analogue scale with response options ranging from 0=No [stress] to 10=Extreme [stress]. Items measure stress present over the past week, ability to cope with stress, fatigue, and level of distress. The Visual Analogue Scale is a standard measure used in the 3RP program.

**5.2.3c. COVID-19 Measures.** The COVID-19 supplementary questions are ten short questions that ask participants to reflect on their experience during the COVID-19 pandemic. This form will help us to interpret their responses to the battery of other psychosocial measures (listed in 5.2.3b) we are administering. This measure will be administered to participants in all upcoming surveys. To minimize burden, participants who have completed the study or any previous study surveys will not be asked to retroactively complete these measures.

**5.2.3d Participant Locator Form** The participant locator form (Appendix 8.28) is a single page form that participants will complete upon consenting for the study. This form asks a variety of questions about communication preferences for the duration of the study. Participants will be reminded that their communications preferences may change during the study, and they should let the study team know of any changes they decide.

**5.2.4. Qualitative Exit Interviews:** A randomly selected subset of study participants (N= approximately 30) will be invited to participate in one-on-one exit interviews after study completion (i.e., they have no more scheduled intervention sessions or follow up surveys) (Appendix 8.29). We are aiming to interview up to approximately 30 AYAs to ensure we capture a wide range of responses. Exit interviews may be completed over the phone or via Partners Telehealth videoconferencing, to explore additional barriers or facilitators to study participation, treatment adherence, program engagement, and study completion. Participants will be asked more detailed information about perceptions of the treatment and preferences for further adaptation after having participated in the program. A series of questions will be asked about using social media outreach for future research recruitment. We will also ask participants to report on how COVID-19 may have impacted their stress levels or ability to participate in the intervention. These interviews will be audiorecorded and

qualitatively analyzed for themes which will help to determine whether treatment modifications are needed in future work. It is estimated that the interviews will take approximately 45 minutes to complete. Participants will be informed that the qualitative exit interviews are an optional portion of the study. Participants who do complete a qualitative exit interview will receive \$30.

To supplement these interviews, with up to 25 experts in the care and treatment of AYAs to inform the design of future psychosocial interventions. This will serve to inform the next iteration of this study. Given the low risk nature of these interviews (the overarching goal of informing future trials), we are requesting a waiver of documentation of consent. Instead, to minimize burden, experts will undergo a verbal consent process, as seen in Appendix 8.30. These individuals could include (but are not limited to) oncology clinicians, primary care providers, psychologists, nurses, social workers, and others who are integral to the treatment and post-treatment experience of AYAs. Experts will be invited to complete these optional interviews over the phone or via videoconferencing to help inform future research, but will not receive any compensation for their time. To offer maximum scheduling flexibility, both individual and group interviews will be conducted. Individual interviews will be approximately 30 minutes long and group interviews will be approximately 60 minutes long. These interviews will be audiorecorded and qualitatively analyzed for themes which will help to determine whether treatment modifications are needed in future work. A sample expert interview guide is provided in Appendix 8.30.

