## 2.2. Exploratory Aims:

a) Using a randomized, waitlist controlled design, we will examine the preliminary effects of the 3RP-AYA on stress and stress management among AYAs. Specifically, we will examine the preliminary effects of the 3RP-AYA on psychosocial measures of mindfulness, depressed mood, anxiety and stress collected at three timepoints, as detailed below: T0 (baseline), T1 (IG: posttreatment, WG: baseline2), T2 (IG: 3 month follow-up, WG: posttreatment).

Exploratory *Hypothesis 2.2a:* Compared to the waitlist-controlled group (WG), the immediate start intervention group (IG) will demonstrate greater mindfulness, lower depressed mood, anxiety and perceived stress at post-treatment. Additionally, the immediate start intervention group (IG) and waitlist control group (WG) combined will demonstrate greater mindfulness, less depressed mood, anxiety and perceived stress at treatment completion (T0-T1 for IG; T1-T2 for WG).

b) We will explore the feasibility and acceptability of collecting hair samples to examine intervention-related changes in cortisol, a stress biomarker. *Exploratory Hypothesis 2.2b2b:* The 3RP-AYA group will demonstrate lower stress reactivity (as manifested by hair cortisol) at timepoint 1 (post-treatment for IG; baseline/waitlist period for WG).

c) In efforts to inform the literature and guide future studies on engaging AYA in psychosocial treatment, we, we will examine AYA reasons for deciding not to participate in this behavioral trial. *Exploratory Hypothesis 2.2c: Participants approached about the study who choose not to participate will do so for a variety of reasons, such as time constraints.*

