**5.4.3 Waitlist Control Group.** The waitlist control design allows all participants who enroll in this study the opportunity to get the 3RP-AYA. Participants in the Waitlist Control Group will be enrolled and complete baseline at the same time as the 3RP Intervention Group, and they will will complete the baseline a second time after the immediate start group completes the 3RP-AYA to allow for pre-post treatment group comparisons (T0 vs T1). The waitlist control group will also complete an assessment after receiving the 3RP-AYA treatment to examine pre-post treatment changes in exploratory measures (T1-T2).

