## 5.6 Description of Study Process

**5.6.1 Instrument Administration:** The Baseline (Timepoint 0), Post-3RP (Timeline 1), and 3-month Follow-up (Timeline 2) Questionnaires will be self-administered by participants either on paper or electronically via REDCap survey in accordance with patient preferences. Patients may also elect to complete the questionnaires at home and mail them back to the study staff in a stamped, pre-addressed envelope, or complete them with a member of study staff over the phone, via secure videoconferencing, or in clinic. Patients may be recruited for the study and enrolled when they become available for an upcoming intervention or WCG session in the future. As outlined in Section 4.4, participants will not be registered on the study until they complete the baseline questionnaire and are randomized. The Timepoint 1 (Post-3RP data collection for the intervention group and baseline data collection for the WCG) may be completed up to approximately 12 weeks (+/- 2 weeks) after Timepoint 0, and Timepoint 2 (Follow-up data collection for the intervention group and Post-3RP data collection for the WCG) may be completed approximately 24-weeks (+/- 2 weeks) after Timepoint 0.

**5.6.2 Hair Cortisol:** Similar to other studies which have utilized hair sample collection for cortisol measurement (Partners IRB Protocol#: 2016P001622; DF/HCC #17-063), participants will be asked to cut a small amount of hair (approximately 150 strands, which is about the diameter of a pencil eraser) as close to the scalp as possible (about 3 cm), and from the back of their head. They will be asked to band or tie the strands near the scalp end, place on the sample in aluminum foil, and return in an envelope to MGH. Participants will be sent detailed sampling instructions (Appendix 8.16) and stamped, addressed envelopes to facilitate mailing. Study staff will explain the purpose of hair collection to participants to facilitate transparency of the study and invite participants the opportunity to learn more about their stress levels. A member of study staff will review the sampling procedures in detail with participants either in-person at MGH or during the brief test call, according to patient preferences and availability. Participants will be asked to provide hair samples at Timepoints 0 and 1. Participants will also be provided with the Hair Cortisol Results

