### **6.8.3 Exploratory Aim c) To explore the feasibility and acceptability of collecting hair samples to examine changes in stress reactivity.**

Feasibility and acceptability: Feasibility metrics for the hair sampling include hair return rates. For measures of acceptability, response frequencies will summarize quantitative feedback from question 13 on the 3RP-AYA Acceptability Questionnaire (Appendix 8.15) about the acceptability of hair collection procedures. Together with qualitative feedback from the Exit Interviews (Appendix 8.29), this information will be used to inform the feasibility and acceptability of hair cortisol measurement.. Hair cortisol samples will be analyzed by [name] laboratory at the University of Massachusetts, Amherst.

Preliminary effects: We will examine group differences in HCC at T1 using independent samples T-tests. Pearson correlation or Spearman's rank correlation will examine the association of HCC with each of our psychological outcomes, controlling for potential confounders.

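### Section 5.2.3a times the second hair sample by the end of the intervention, which for the waitlist arm reads as T2, although the planned cortisol comparison needs T1 in both arms

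*Combined protocol and SAP*

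**What the plan says.** Section 5.2.3a, which describes what participants are told to do, sets the two samples as follows: "Participants will be instructed to provide one hair sample at baseline and one sample at the end of the intervention". Section 5.6.2, on study procedures, says: "Participants will be asked to provide hair samples at Timepoints 0 and 1". Neither sentence distinguishes the arms.

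The meaning of each timepoint by arm is given elsewhere. Section 5.4.3 has the waitlist arm "complete the baseline a second time after the immediate start group completes the 3RP-AYA", which is T1. Section 5.6.1 describes "Timepoint 2 (Follow-up data collection for the intervention group and Post-3RP data collection for the WCG"), so the waitlist arm's own post-programme assessment is T2. On timing, 5.6.1 says T1 "may be completed up to approximately 12 weeks (+/- 2 weeks) after Timepoint 0" and T2 "may be completed approximately 24-weeks (+/- 2 weeks) after Timepoint 0".

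The cortisol hypothesis in 2.2b is placed "at timepoint 1 (post-treatment for IG; baseline/waitlist period for WG"). The analysis in 6.8.3 matches it: "We will examine group differences in HCC at T1 using independent samples T-tests".

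The schedule in 5.5 marks hair at baseline and in the Post-3RP column, and not in the 3-Month Follow-Up column.

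**The concern.** The two sampling rules broadly agree for the immediate-start arm and disagree for the waitlist arm. A waitlist participant who is told to send the second sample when the programme ends would send it at about T2, after eight sessions, and would send nothing at T1.

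The between-group test in 6.8.3 is the only planned between-arm comparison of cortisol, and it relies on the waitlist arm being untreated when sampled. Each waitlist participant sampled only at T0 and T2 drops out of that test. The late sample cannot stand in for the missing one, because it reflects a period in which that person was receiving the programme.

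**Working it through.** **1. Meaning of each rule by arm**

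| Rule | Immediate-start arm | Waitlist arm |
|---|---|---|
| 5.2.3a: end of the intervention | about T1 | literally T2, after the programme |
| 5.6.2: T0 and T1 | T1 | T1, second baseline, before the programme |
| 2.2b: hypothesis | T1, post-treatment | T1, waiting period |
| 6.8.3: test | T1 | T1 |

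The agreement for the immediate-start arm is approximate. The course lasts about 8 weeks (5.4.1), while T1 may fall as late as about week 12 (5.6.1).

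**2. Reading the 5.5 schedule.** Its column headings do not name arms. The row for the acceptability questionnaire settles their meaning: it is due in the Post-3RP column for the intervention arm only and in the 3-Month Follow-Up column for the waitlist arm only. Since the waitlist arm answers that questionnaire after its own programme, at T2, the columns must be T1 and T2 labelled from the immediate-start arm's side. A hair mark under Post-3RP therefore means T1 in both arms. That has to be inferred, because 5.6.1 uses the same term for the waitlist arm at T2.

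**3. Size of the timing gap in the waitlist arm.** Inputs from 5.6.1: T1 at week 12 ± 2, T2 at week 24 ± 2.

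- Nominal: 24 − 12 = 12 weeks.
- Shortest: (24 − 2) − (12 + 2) = 22 − 14 = 8 weeks.
- Longest: (24 + 2) − (12 − 2) = 26 − 10 = 16 weeks.

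Section 5.6.1 gives the T1 time as an upper figure, so an earlier T1 would lengthen the gap further.

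**4. What a late sample would measure.** Inputs: growth of about 1 cm a month (5.2.3a) and a sample of about 3 cm, as 5.6.2 can be read. The look-back is 3 cm ÷ 1 cm per month = 3 months, or about 13 weeks. At week 24 that covers about week 24 − 13 = 11 to week 24, which is nearly all of the interval from T1 to T2, when the waitlist arm is treated. At week 12 it covers essentially the waiting period.

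**5. Number exposed.** An equal split of 72 gives 72 ÷ 2 = 36 per arm, and 5.1 aims for 30 completers per arm. So 30 to 36 is the most that could be affected. The actual number cannot be derived from the documents.

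**6. Adjusting for T0 (a separate matter).** With a linear adjustment and correlation r between T0 and T1 cortisol, residual variance is multiplied by 1 − r². The documents give no r. As an assumed range, r = 0.3 gives a reduction of 0.3² = 9%, and r = 0.7 gives 0.7² = 49%.

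**The case against.** The best defence is that this is one loose sentence in a plan that is otherwise consistent. The heading of 5.2 sends the reader to 5.5 for the schedule, so 5.2.3a is not the controlling text. Hypothesis 2.2b, 5.6.2 and 6.8.3 state T1, and 5.5 implies it. The protocol often labels timepoints from the immediate-start arm's side, so the intervention in 5.2.3a may simply mean that arm's course; 5.4.3 ties the waitlist arm's second baseline to the same event. Study staff also review the sampling procedure with participants (5.6.2), who do not work from 5.2.3a themselves. All of this stands, and it limits the point to a risk in execution.

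A reader might infer that the T1 comparison has no control arm, or that treated participants will be compared with treated. The documents do not support either. Losing the whole arm would require staff to overlook four other places. Hair sampling is optional (5.6.4) and is not done after recent glucocorticoid use (5.2.3a), so the number exposed is probably below the ceiling anyway. No section plans to use a T2 sample in place of a T1 sample. The instruction sheet, Appendix 8.16, is not in the text available for review and may already give the timing correctly.

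Nor is the t-test wrong. Comparing randomised arms at T1 without adjustment is valid, and the timing conflict gives no reason to change it. Adjustment is a choice about precision.

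What the defence does not remove is that 5.2.3a describes what participants will be told, gives no arm-specific timing, and read literally sends waitlist participants to a different timepoint.

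**Conclusion.** The conflict is real and its consequence is modest. Read literally, 5.2.3a places the waitlist arm's second sample nominally 12 weeks after T1, with a range of 8 to 16 weeks from the stated windows. The intended rule, T1 in both arms, can be recovered from the rest of the plan. What remains is a risk that an unknown number of waitlist participants are mistimed and supply no untreated value to the T1 comparison.

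Severity is low. The outcome is exploratory, and the primary endpoints of programme feasibility and acceptability are not affected. The conclusion rests on two assumptions: that the intervention in 5.2.3a can be taken to mean each participant's own course, and that Appendix 8.16 does not already settle the matter. The look-back argument also assumes that the 3 cm in 5.6.2 is the length of hair sampled.

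**What to change.** - In 5.2.3a, state: one sample at T0 and one at T1 in both arms; for the waitlist arm T1 precedes the programme.
- In 5.5, relabel the Post-3RP column as T1, with its meaning for each arm, and the 3-Month Follow-Up column as T2 in the same way.
- Check that Appendix 8.16 gives the same timing, and amend it only if it does not.

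The cost is a sentence, two column labels and a check of one appendix. No sample, visit or payment is added.

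As a separate, optional improvement, replace the unadjusted t-test in 6.8.3 with a comparison of T1 cortisol between arms that has the T0 value as a covariate. The T0 sample is already collected, so only the analysis text changes. That text should say how participants with a T1 but no T0 sample are handled; the multiple imputation already named in 6.9 could be extended to them.

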## 5.5 Data Collection and Storage.

Prior to study enrollment, study data will be collected via medical record review for Partners patients or through patient self-report, if no available EMR through the Partners Healthcare System, at screening to determine study eligibility. In addition, we will gather descriptive information about our sample via brief surveys and assess levels of the stress hormone cortisol via hair sample collection. Specifically, we will collect data on:

Data	At Screening	At Baseline	At 3RP	At Post-3RP	At 3-Month Follow-Up
Date of birth	x				
Gender	x				
Languages spoken	x				
Cancer diagnosis	x				
Date of diagnosis	x				
Treatment type(s)	x				
Date of treatment completion	x				

Data	At Screening	At Baseline	At 3RP	At Post-3RP	At 3-Month Follow-Up
Demographic factors		x			
Psychosocial measures:					
Visual Analog Scales		x		x	x
Intolerance of Uncertainty Scale		x		x	x
Measure of Current Status – Part A (MOCS-A)		x		x	x
Patient-Reported Outcomes Measurement Information System (PROMIS) Measures		x		x	x
Coping Self-efficacy Scale		x		x	x
Health Behavior Questions		x		x	x
Penn State Worry Questionnaire (PSW-Q)		x		x	x
Interpersonal Reactivity Index		x		x	x
Current Experiences Scale (CES)		x		x	x
Hair cortisol measurement		x		x	
3RP acceptability questionnaire				x (intervention arm only)	x (waitlist arm only)
Weekly RR practice logs (Appendix 8.27)			x		
COVID19 Supplementary Questions		x		x	x
Optional Exit Interview (Appendix 8.29)					x (after completion of all study measures)

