## **6.8 Analysis Plan.**

### **6.8.1 Aim a) To examine the feasibility and acceptability of a group-based, stress-management and resiliency intervention delivered via videoconferencing technology for adolescent and young adult cancer survivors who are within 5 years of having completed cancer treatment.**

Descriptive statistics, including means, frequencies, and ranges will be used to describe the sample and to summarize feasibility, acceptability, and program satisfaction. Feasibility outcomes will be assessed by determining the proportion of individuals who were recruited, screened, and enrolled in the study. Response frequencies will summarize reasons for ineligibility and refusal. We will also determine the proportion of enrolled participants who complete the study. Participants who complete at least 75% of the treatment sessions (6 out of 8 sessions) will be identified as treatment completers. We will examine the proportion of individuals who attend each session and the percent that adhere to recommended RR practice (defined as RR elicitation at least 3 days/week). For acceptability, response frequencies will summarize quantitative feedback on the 3RP-AYA Acceptability Questionnaire (Appendix 8.15). Together with qualitative feedback from the Exit Interviews (Appendix 8.29) and Expert Interviews (Appendix 8.30), this information will be used to inform the feasibility and acceptability of the intervention.

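### Exit interviews are meant to explain non-adherence and non-completion, but the plan does not settle whether people who leave measures incomplete can be interviewed, and a random draw would reach few of them

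*Combined protocol and SAP*

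**What the plan says.** Section 5.2.4 sets out selection, timing and purpose.

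- **Selection:** "A randomly selected subset of study participants (N= approximately 30) will be invited to participate in" an optional interview. No stratification by attendance or completion status is described.
- **Timing:** "one-on-one exit interviews after study completion (i.e., they have no more scheduled intervention sessions or follow up surveys").
- **Purpose:** "to explore additional barriers or facilitators to study participation, treatment adherence, program engagement, and study completion".

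The data collection table in section 5.5 puts the interview in the 3-month follow-up column with the note "after completion of all study measures".

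Section 6.8.1, the analysis of the primary aim, uses the interviews as evidence alongside the acceptability questionnaire: "this information will be used to inform the feasibility and acceptability of the intervention".

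Three other provisions bear on the point. Section 6.9 lets people who no longer want sessions complete the follow-up assessments. Section 6.8.1 defines a treatment completer by attendance (6 of 8 sessions), which is separate from returning surveys. Section 5.1 promises to examine who does not complete and in what circumstances, but names no instrument for doing so.

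**The concern.** A pilot of this kind needs to learn why people stop attending or leave. The exit interview is the only named instrument that asks enrolled participants directly about barriers to adherence and completion. If its sampling frame is restricted to people who finished every measure, those best placed to answer are outside it. If the frame is everyone, a draw that ignores attendance and completion reaches them only in proportion to their number, which is expected to be small.

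The acceptability questionnaire does not close the gap. It is given with the post-treatment survey in each arm (T1 for immediate start, T2 for waitlist), so a person who misses that survey is missing there too. The reasons collected under sections 2.2c and 5.2.2 come from people who are ineligible or refuse, not from enrolled participants who later stop. Both sources used for acceptability could therefore lean toward those who stayed.

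**Working it through.** No figure in the plan is in dispute here. The check is a comparison of the passages, followed by an illustrative calculation.

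**1. Who is in the frame under each reading**

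| Participant | 5.5 entry read as a condition | 5.2.4 wording (nothing further scheduled) |
|---|---|---|
| Attended 6 or more sessions, all measures returned | in | in |
| Stopped sessions or attended few, all measures returned (section 6.9) | in | in |
| Missed a survey, remained in the study | out | in, once nothing further is due |
| Withdrew or was lost | out | could be in; not stated |

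The readings differ only in the last two rows, so those are the people the gap concerns.

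**2. Inputs for the illustration**

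- N = 72 enrolled (sections 2.1, 5.1 and 6.2).
- n = 30 invited (section 5.2.4).
- D = number of non-completers. The plan gives no forecast of incomplete measures. Section 6.2 allows for 72 − 60 = 12 people who attend no session (12/72 = 16.7%). I use D = 12 as a stand-in and assume D = 6 and D = 18 as a range.

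**3. Condition reading**

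If the D people leave measures incomplete, none can be invited: 0 of 30, whatever D is.

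**4. Generous reading: all 72 in the frame, simple random draw**

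The number of non-completers invited is hypergeometric with mean n × D/N. Each person's chance of invitation is 30/72 = 41.7%.

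| D | Mean invited | 95% range |
|---|---|---|
| 6 | 30 × 6/72 = 2.5 | 0 to 5 |
| 12 | 30 × 12/72 = 5.0 | 2 to 8 |
| 18 | 30 × 18/72 = 7.5 | 4 to 11 |

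For D = 12 the probability of inviting 2 or fewer is 5%; for D = 6 it is 51%. These are invitations to an optional interview, so completed interviews may be fewer.

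**5. When reserving places changes anything**

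A random draw from all 72 would already average 10 invitations to a group of size 10 × 72/30 = 24. Reserving 10 places therefore raises the expected number of invitations only if the group has fewer than 24 members. If it has fewer than 10, all can be invited and the remaining places revert to completers.

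**The case against.** The strongest reply has four parts.

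- **The 5.5 entry may be only about timing.** It sits in a timing grid, and 5.2.4 supplies the working definition. Read literally as an eligibility rule, it would also bar participants who decline the optional hair sample (section 5.6.4) or from whom none is taken because of glucocorticoid use (section 5.2.3a), which can hardly be intended. This is a fair reading. It does not remove the need to align the two places, because staff working from the schedule could apply it as a condition.
- **Stopping sessions is not leaving the study.** This stands. A reader might infer that dropouts as a class are never interviewed; section 6.9 rules that out. People who stop attending but return surveys remain eligible, so some barriers to adherence can be heard under either reading.
- **Non-completion is examined elsewhere.** Section 5.1 promises to look at its circumstances, section 4.4 requires a note to file on lost participants, and sections 6.8.2 and 6.9 compare completers with non-completers. These help, but the note to file is a staff record, the comparisons describe characteristics rather than reasons, and section 6.8.1 does not name the note among its sources.
- **Proportional selection is not an error.** Correct: a random draw represents a group according to its size. The argument for stratifying is that it serves the stated purpose better, not that random selection is invalid.

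It is also true that the quantitative feasibility threshold is session attendance (section 6.2), with interviews only in support, and that someone who attended no session cannot rate the content. Such a person can still say what kept them away.

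**Conclusion.** The point holds as a misalignment between sections 5.2.4 and 5.5, together with a selection method poorly matched to the purpose of the interviews. It mainly affects participants who leave measures incomplete. Under the condition reading none of them can be interviewed. With all 72 in the frame, about 5 of an assumed 12 would be invited (95% range 2 to 8), with means of 2.5 and 7.5 if there are 6 or 18.

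The value 12 is borrowed. Section 6.2 defines that loss as attending no session, which is not the same as leaving measures incomplete, and section 5.1 says that people who attend no intervention visit do not count toward the 72. The calculation shows the order of magnitude and is not a forecast.

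A reader might also infer that acceptability will be overstated by a known amount. Upward bias is plausible, but nothing in the documents quantifies it. Because the interviews are optional and qualitative yet inform the primary conclusion, this is a low-cost improvement worth making. Confidence is moderate.

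**What to change.** 1. Reword the section 5.5 entry to match 5.2.4: the interview takes place once no further sessions or surveys are due, including after withdrawal or loss to follow-up.
2. State in 5.2.4 that participants who withdrew, were lost or attended few sessions are in the interview frame unless they decline further contact.
3. Replace simple random selection with selection stratified by attendance and completion status. Reserve a share of the same 30 places for participants with fewer than 6 of 8 sessions or no final survey; about 10 is an illustrative number, not a derived one. Fill the rest at random from completers, and let unfilled reserved places revert to them.
4. Report themes separately for the two groups, since the combined set would no longer mirror the enrolled sample.

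The cost is protocol wording. The number of interviews and the $30 payment do not change. The drawback is that non-completers are harder to reach, so some reserved places may go unfilled.
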